4.0 Inclusion and Exclusion Criteria

NOTE: If your study is more than minimal risk, you must also upload (in the myResearch IRB smartform) a copy of your inclusion/exclusion checklist to be completed at time of enrollment of each subject.

4.1 Describe, in bullet points, the criteria that define who will be included in this study.

Response: Please see inclusion/exclusion attachment for details. In brief, however:

- Adults aged 65+ years who reside at Jefferson's Ferry independent living.
- Express interest in the ankle wearable device.
- Individuals who can communicate in English and provide written consent.
- •They must have capacity as measured by being alert and oriented to person, place, and time.
- Participants are able to walk and stand unsupported by others and feel ankle vibrations from the Accelera device at maximum amplitude.

- Answer Yes to at least one: worry about falling, had a fall within last year, feel unsteady when walking, limit activity due to fear of falling, enrolled in a fall prevention program, or use or have used assistive devices for ambulation (e.g. canes or walkers).
- 4.2 Describe, in bullet points, the criteria that define who will be excluded from this study.

Response: Please see inclusion/exclusion attachment for details. In brief, however:

- Patients diagnosed with neurodegenerative diseases (such as Parkinson's, Alzheimer's, or ALS)
- Any lower extremity amputation other than one toe
- Disability from a stroke or other major neurologic disorder resulting in leg paralysis
- Active ulcers/rashes/infections on feet or legs, or using orthotics other than arch supports or over the counter knee/ankle supports
- Significant lymphedema/peripheral edema/or large ankle size that prevents ankle wearable device application or functionality
- Unable to participate due to other medical or cognitive reasons.
- Cannot give written consent.
- · Cannot walk today or generally use wheelchairs
- On anticoagulants or antiplatelet agents other than aspirin
- Age under 65 years
- ** Individuals with any active infection and/or currently receiving prescribed antimicrobial agent(s) will be asked to return when infection is resolved.
- 4.3 Describe how individuals will be screened for eligibility. Upload all relevant screening documents with your submission (screening protocol, script, questionnaire). Identify who will certify that subjects meet eligibility requirements. (Upload these documents in the myResearch IRB smartform.)

Response: Participants who are interested will be able to sign up at their discretion after the study is presented to the Jefferson's Ferry community.

To be included, please see detailed inclusion/exclusion criteria attachment. However, in brief they will need to:

- Answer Yes to at least one: worry about falling, had a fall within the last year, feel
 unsteady when falling, enrolled in a falls prevention program (past and/or present), or
 use in the past year of assistive devices for ambulation (e.g. canes and/or walkers)
- Are you willing to wear a device on both ankles for up to 1 hour at a time?
- Are you able to commit to completing the pre and post study questionnaire, 3 mobility tests before and while wearing the ankle bracelets.

• The intake form will also contain additional demographic questions (see attached).

5.0 Vulnerable Populations

5.1 and up	For research that specifically recruits/targets minors (under 18 years), review, complete bload Supplemental Form F: Minors.
	Confirmed
⊠ consei	N/A: This research does not involve persons who have not attained the legal age for nt to treatments or procedures ("children").
5.2 you wi	For research that specifically recruits/targets adults who cannot consent for themselves, ll be asked additional information in Section 25 ("Informed Consent").
	Confirmed
	N/A: This research does not involve this population.
•	For research that specifically recruits/targets pregnant women, review, complete and Supplemental Form A: Pregnant Women, Fetuses, Non-Viable Neonates, or Neonates ertain Viability.
	Confirmed
\boxtimes	N/A: This research does not involve pregnant women.
	For research that specifically recruits/targets neonates of uncertain viability or non-viable tes, review, complete and upload Supplemental Form A: Pregnant Women, Fetuses, iable Neonates, or Neonates of Uncertain Viability.
	Confirmed
⊠ viabilit	N/A: This research does not involve non-viable neonates or neonates of uncertain y.

Protoc	ol Title (Running Head):	
5.5 Supple	For research that specifically recruits/targets prisoners, review, complete and upload emental Form B: Prisoners.	
	Confirmed	
	N/A: This research does not involve prisoners.	
informa	Consider if other specifically targeted populations such as students, employees of a c firm, or educationally or economically disadvantaged persons are vulnerable. Provide ation regarding their safeguards and protections, including safeguards to eliminate on or undue influence.	
Safeguards include:		
	N/A: This research does not involve these populations.	
6.0 Recruitment Methods		
	N/A: This is a records review only, and subjects will not be recruited.	

NOTE: If you select this option, please make sure that all record review procedures and inclusion/exclusion screening are adequately described in other sections, including date range for records that will be reviewed.

6.1 Describe source of subjects: When, where, and how potential subjects will be recruited. In order to approach patients in the clinic/hospital setting you must have a treatment relationship with these individuals.

NOTE: Recruitment refers to how you are identifying potential participants and introducing them to the study.

Response: Participants for this pilot study will be older adults (age>=65 years) living at Jefferson's Ferry Independent Living, who use or have used an assistive device for ambulation in the past year, who are interested in trying this technology, and meet detailed inclusion/exclusion criteria evaluation as per the checklist. Before enrollment, as a part of Jefferson's Ferry monthly meeting calendar, it will be indicated that an in-person educational session on this proposed study will be held. Study team members will then provide an educational session at Jefferson's Ferry to describe the study and invite eligible residents to participate. As the plan is to conduct enrollment and study sessions on one day of the week

(tentatively Mondays), excluding holidays or other institutional/researcher obligations, those interested would also be advised that they can stop in on study days for screening/enrollment.

6.2 Describe how you will protect the privacy of prospective subjects during the recruitment process.

NOTE: Examples of appropriate responses may include: "participant only meets with a study coordinator in a private office setting where no one can overhear", "the participant is reminded that they are free to refuse to answer any questions that they do not feel comfortable answering."

Response: During the recruitment and screening process, participants' privacy will be protected by ensuring that all recruitment activities occur in a confidential manner. This includes discussion of recruitment and consent in a private consultation room at Jefferson's Ferry. Interested individuals will contact the study staff directly to express interest. Personal discussions regarding the study will take place in private settings, in person, to ensure privacy. Only authorized research staff will be involved in the recruitment and screening process. There is only 1 educational session planned. We would have a sign-up sheet for those who are interested at the end of the session and provide them with information about when the study sessions will be taking place so they can further assess interest and eligibility. People interested can also come to the Wellness Center on days that the study is being performed to express their interest.

In addition, all participant information collected during the subsequent screening process will be de-identified and stored securely. The research team will use a unique identifier for each participant, and all identifiable information (i.e. the consents) will be kept in locked cabinets accessible only to designated research personnel until it and the other forms can be uploaded to the University's secure share drive system. At that point, the physical copies will be destroyed. Furthermore, electronic records will be stored on password-protected, encrypted Stony Brook Medicine servers to prevent unauthorized access.

7.0 Research Procedures

- 7.1 Provide a detailed description of all research procedures or activities being performed on the research subjects. This should serve as a blueprint for your study and include enough detail so that another investigator could pick up your protocol and replicate the research. For studies that have multiple or complex visits or procedures, consider the addition of a schedule of events table in in your response. Be sure to include:
- Procedures being performed to monitor subjects for safety or to minimize risks.

· All drugs and devices used in the research and the purpose of their use, and their regulatory status

Response: The intervention involves the collection and analysis of data from older adults (age 65+) living at Jefferson's Ferry independent living to evaluate the effects of stochastic resonance (SR) ankle wearables on gait and mobility. The device will be applied during a study session lasting about 1.5-2 hours, where about 1 hour is spent on completing the pre- and post-study questionnaires on pen/paper. The other 1 hour is spent on the various gait and mobility evaluations before and while wearing the device, as detailed below.

At the visit, after completing the pre-study questionnaire, participants will perform 3 tests validated by the CDC for fall risk screening: the timed up and go test, 30-second chair stand, 4 stage balance test. If the participants opt in to mobility analysis performed with the Onform iPad/iPhone video recording app without the participant's name, rather than with a code, then this would be performed. As indicated above, participant's faces will be obscured. The ankle bracelets will then be applied. After about 30 minutes of resuming their usual ambulation in the observation area as below, the same 3 tests would be repeated as well as if they had opted in above, repeat mobility video recording with the Onform app, all while the ankle bracelets are in place. The ankle bracelets will be removed after completion of the session. Before application of the Accelera device and while they are wearing the Accelera device, the participants will be asked to continue to use their usual mobility assistive devices as they usually do. The post study questionnaires will then be completed. All questionnaires will be completed with pen/paper.

There will generally be 1 session per week at Jefferson's Ferry, at the Wellness Center/gym or other designated area at Jefferson's Ferry, with a minimum of one patient for up to 8 patients/week if no holidays, until 20 patients have completed the study. It is currently tentatively planned for Mondays, excluding holidays and other institutional/researcher availability requirements. However, this may be adjusted in coordination with Jefferson's Ferry.

Possible participants will be able to sign up at the educational session for additional information. Additionally, they will be advised that they can come sign up at any date that we are having a study session. They would only complete the screening/survey questionnaires at a study session.

If the participants opt in, then the app that will be used for mobility analysis during the study is called Onform, from Onform Inc. It is a HIPAA compliant video recording and analysis App. The video recording that is saved will be saved as per the app specifications using a first and last name, however the first name will be the 1st digit of the subject ID code, and the last name will be the last digit of the subject ID code. As indicated above, participants' faces will be obscured. Analysis will be as described in section 3.7 above. Please see the attached app privacy policy.

7.2 Describe what data, including long-term follow-up data, will be collected.

NOTE: For studies with multiple data collection points or long-term follow-up, consider the addition of a schedule or table in your response.

Response: The data being analyzed includes participant pre and post study questionnaires, including demographics, sensory thresholds for the Accelera device, 30-second chair stand, 4 stage balance test, and timed up and go (TUG) task outcomes. There will also be mobility/gait/posture analysis performed via an iPad/iPhone App without the participant's name before and while wearing the ankle bracelets. Researchers will provide basic prompts regarding participants' stability and gait. Participants will also complete a self-reported health/exercise/fear of falling questionnaire at the start of the visit and at the end of the visit as well as a post questionnaire. We will also evaluate for falls with or without the device at the study session. There is no long-term follow-up.

7.3 List any instruments or measurement tools used to collect data (e.g., surveys, scripts, questionnaires, interview guides, validated instruments, data collection forms). Upload these materials in the myResearch IRB smartform.

Response: Participants will complete a self-reported health/exercise/fear of falling/mobility questionnaire as detailed above during the index visit and at the start and end of the study session. Their performance on the above 3 CDC tests (the chair stand test, 4-point balance test, and timed up and go test) will be measured and recorded using the CDC defined evaluation tool before and while wearing the ankle bracelets. If the participants opted in, then we will also perform gait/mobility analysis with the HIPAA compliant Onform app, as indicated above in section 3.7, before and while wearing the ankle bracelets. We will also measure sensory thresholds for the Accelera device. Finally, we will also evaluate for falls with or without the device at the study session.

7.4 Describe any source records that will be used to collect data about subjects (e.g., school records, electronic medical records) and include the date range for records that will be accessed.

Response: Participants will be asked to list their medical histories in the questionnaire indicated above, assistive device use, and fall history/fear of falling. The study team will not access any patient medical records. Please see attachment for detailed intake form questions.

7.5 Indicate whether or not the results for individual subjects, such as results of investigational diagnostic tests, genetic tests, or incidental findings will be shared with subjects or others (e.g., the subject's primary care physician) and if so, describe how these will be shared.

Response: The participants will be advised of their performance on the 3 CDC tests (the chair stand test, 4-point balance test, and timed up and go test) before and while wearing the ankle bracelets, their responses on the pre and post questionnaires as well as mobility/posture/gait analysis app findings if participants want to review these.

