assistance devices, if any. In other words, a video recording is made with the app and stored on the apps' HIPAA compliant platform. With the faces obscured, measurements of their gait/mobility will be performed using additional programs as indicated in the Data section. After bracelet application, volunteers will then be encouraged to resume their normal ambulation-(while using their usual mobility assistive devices) for about 30 minutes at the study location as described below. The same 3 tests will be repeated after 30 minutes, along with a post-study questionnaire, and if they consented to video recording above, then repeat videorecording with the Onform video recording app would be performed. With the faces obscured, measurements of their gait/mobility will be performed using additional programs as indicated in the Data section. At this point, the ankle bracelets will be removed – with the subjects having worn them for about 1 hour total. There will be an additional up to 1 hour for completion of the pre- and post-study questionnaires, for a total study session duration of about 1.5 - 2 hours. At each session, we will apply these bracelets to a minimum of 1 patient per session. These sessions will occur at the Wellness Center/gym or other designated area at Jefferson's Ferry 1x per week, with a minimum of one patient for up to 8 patients/week if no holidays, until 20 patients have completed the study. To address infection control, a disposable sock will provide a physical barrier between the device and patient, while still allowing the patient to feel the stochastic resonance.

3.2 Include the number of subjects and the power analysis. If applicable, indicate your screen failure rate, i.e., how many subjects you expect to screen to reach your target sample.

Response: 20 volunteers will be enrolled. The study would continue until 20 volunteers are enrolled and complete all non-optional parts of the single study session.

3.3 Indicate the duration of the subject participation including long-term follow-up.

Response: A single study session. There is no long-term follow-up in this study.

3.4 Indicate whether you are specifically recruiting or targeting any of the following special populations in your study using the checkboxes below.

Response: n/a

Minors (under 18 years old)

Adults unable to consent

Pregnant women

Protoco	ol Title (Running Head):
	Prisoners

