	Indicate if you will include minorities (American Indians, Alaskan Native, Asian, Native an, Pacific Islander, Black [not of Hispanic origin] and Hispanic) as Federal mandates that you include minorities unless you can justify their exclusion.
Respor	nse:
\boxtimes	Yes
	No, Justify:

3.6 Indicate whether you will include non-English speaking individuals in your study. Provide justification if you will specifically exclude non-English speaking individuals. Review https://www.stonybrook.edu/research-compliance/Human-Subjects/sops for the SBU policy on inclusion of non-English speakers (section 17.8). Following approval of the English version, you must submit the translated version of the materials with the attestation of the translation.

Response: Non-English speakers will be excluded to assure understanding of verbal instructions in English as well as enable completion of the survey.

3.7 Describe the data analysis plan, including any statistical procedures.

NOTE: If we are a lead site for a multi-site study include the total number of subjects that will be enrolled, or records that will be reviewed across all sites. This section applies to both quantitative and qualitative analysis.

Response: The data of participants who meet the inclusion criteria will be collected during study visits and recorded directly by study staff. Only the consents will have the participant's names. There will be no linking of the participant to subject ID. Hence, all data will be de-identified and stored using unique study identifiers to protect participant privacy. The data will be securely stored on password-protected, encrypted servers at Stony Brook Medicine to ensure compliance with privacy and confidentiality standards.

If the participants choose to have their mobility evaluated by the research team with the video recording app, then their videos would be uploaded to the HIPAA compliant platform of the app. The first name used for the app would be the 1st digit of their assigned code and the last name would be the last digit of their assigned code. Their faces would be obscured by taking a video from the chin/neck down.

Descriptive Analysis:

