Descriptive univariate statistics will be conducted to summarize the demographic and performance characteristics of the study population, including device sensory thresholds, gait/mobility using a mobility videorecording app (optional, see below) before and while wearing the ankle bracelets, pre- and post-study questionnaires, and performance before and while wearing the ankle bracelets on the 3 CDC STEADI tests (the chair stand test, 4 point balance test, and timed up and go test). Multivariate analysis would also be performed.

Videos uploaded on the Onform app with participants' faces obscured would then be analyzed with additional feature extraction, analytics, and statistical programs. This would include optical character recognition programs to analyze the joint angles numbers that the video recording provides. Outside of the app, parts of the video will be cropped, the stick figure that the Onform app generates will be highlighted, and the contrast and lighting of the video will be adjusted to make the subject look like a shadow, ie s no features of the subject (such as clothing, gender, skin color, etc.) can be recognized. Programs such as ImageJ will be used for feature extraction. Python/R will be used to pull the data from the videos/cropped images. Python/R/excel will be used for statistical analysis of gait/mobility parameters, such as joint angles, stride time, stance time, swing time, cadence, stride length, step width, and foot angle, etc

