12.0 Confidentiality

A. Confidentiality/Security of Study Data

Describe the local procedures for maintenance of security and confidentiality of study data and any records that will be reviewed for data collection.

NOTE: Confidentiality refers to how data collected about individuals for the research will be protected by the researcher from release. Confidentiality applies to the data.

12.1 Where and how will all data and records be stored? Include information about locked cabinet/locked office, authorization of access, certificates of confidentiality, and separation of identifiers and data, as applicable. Include physical (e.g., paper) and electronic files (e.g., storage of data in REDCap) password protection, encryption.

Response: All data and records will be stored locally on secure Stony Brook Medicine networks. The only identifying data is the consent form. However, this will not be linked to the unique random study code/participant id number. The data will be collected during study visits and deidentified, with participant identifiers being replaced by unique study codes. The de-identified data will be encrypted and securely stored on Stony Brook Medicine encrypted servers, which meet institutional security standards. Access to the data will be restricted to authorized personnel, with password-protected systems and encryption in place to ensure data security. Additionally, all identifiable information, such as consent forms will be uploaded to a secure

Stony Brook Medicine shared drive and then disposed in the secure Health Sciences Center (HSC) discard bin.

The optional Onform app video recordings will be stored on the apps HIPPA compliant platform. The face will be obscured.

The physical forms (i.e. pre and post questionnaires, performance on the app, CDC tests, device sensory thresholds) will be transported to SBUH by research personnel and will be stored separately in a secured, locked file cabinet until they can be uploaded (scanned) into the secured shared drive, at which point all physical forms will be discarded in the Stony Brook Medicine HSC secure bins. Answers to the study questionnaires, performance on the 3 CDC tests as well as gait analysis app findings, Accelera device sensory thresholds, will also be entered into an excel sheet on the Stony Brook Medicine shared drive.

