13.0 Withdrawal of Subjects			
□ N/A: This study is not enrolling subjects. This section does not apply.			
13.1 Describe anticipated circumstances under which subjects may be withdrawn from the research without their consent.			
Response: if the participant is unable to participate in the study during the study session for any reason, including inability to walk, they would be withdrawn from the study			

13.2 Describe any procedures for orderly termination.

NOTE: Examples may include return of study drug, exit interview with clinician. Include whether additional follow up is recommended for safety reasons for physical or emotional health.

Response: n/a

13.3 Describe procedures that will be followed when subjects withdraw from the research, including retention of already collected data, and partial withdrawal from procedures with continued data collection, as applicable.

Response: If a subject withdraws on the day of the study before information is deidentified, their data will be removed. This includes removal of data/videos from the Onform app if they had opted in to participate.

13.4 Describe what will happen to data already collected.

Response: Data can only be discarded at the time of the study session if the participant requests. After that, we would not be able discard it as there is no matching between the person who signed the consent and the random participant/subject ID. As we are not keeping any picture of the participants and faces will be obscured on the Onform video recording, after the session, we would not be able to delete the videos.

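### Could filing the optional videos under only the first and last digit of the study code mix up participants?

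*Protocol*

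**What the plan says.** The rule appears twice in the Protocol. Section 3.7 (data analysis plan) says "The first name used for the app would be the 1st digit of their assigned code", with the last digit used as the last name. Section 7.1 (research procedures) repeats it: "the first name will be the 1st digit of the subject ID code, and the last name will be the last digit". Section 7.1 also gives the reason for two fields: the app's own specification calls for a first and a last name.

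Section 12.1 describes the code when it says of the consent form: "However, this will not be linked to the unique random study code/participant id number". The code is thus called unique and random, but no section gives its length or says whether it has leading zeros.

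Four other statements bear on the point:

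- **Sample size (Section 3.2):** "20 volunteers will be enrolled".
- **Use of the videos (Section 3.7):** the descriptive analysis covers "gait/mobility using a mobility videorecording app (optional, see below) before and while wearing the ankle bracelets".
- **Session size (Section 7.1):** about one session a week, "with a minimum of one patient for up to 8 patients/week if no holidays".
- **Other records (Section 12.1):** paper forms are kept, including one for performance on the app, and "performance on the 3 CDC tests as well as gait analysis app findings" are entered in a spreadsheet.

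**The concern.** A rule that keeps only the first and last digit of a code discards whatever lies between. With three or more digits, at most 100 names exist, so distinct codes can map to the same name. With one- and two-digit codes and no leading zero, codes 1 and 11 both become 1 / 1. The code's uniqueness would then not carry over to the video file.

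Other ways of telling the recordings apart are weakened on purpose. Faces are not filmed. The images are processed until clothing, gender and skin color cannot be recognised (Section 3.7). There is no key linking people to codes; Section 13.4 says "there is no matching between the person who signed the consent and the random participant/subject ID". Each filmed participant has one recording before and one while wearing the bracelets, so a shared name would put four recordings under one label.

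At stake would be the pairing of a participant's two videos with each other and with the same person's CDC tests, questionnaires and sensory thresholds. Removing the right video when someone withdraws on the day (Section 13.3) could also become harder. The three CDC tests and the questionnaires are not filed under this rule and would be unaffected.

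**Working it through.** The Protocol gives no figure on this point, so there is none to reproduce. The check is to count the names that the rule yields under each plausible code format.

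**Inputs.** Participants: 20 (Section 3.2). Rule: first digit plus last digit (Sections 3.7 and 7.1). Code length and number filmed are not stated, so every format below is an assumption, and the number filmed, *k*, is varied from 5 to 20.

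**Step 1: codes of exactly two digits.** The first and last digits are the whole code. Codes 01 to 20 give 20 names for 20 people, and random distinct codes from 00-99 or 10-99 also never clash. The chance of a shared name is 0 for any *k*.

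**Step 2: codes 1 to 20 without a leading zero.** There are 19 names for 20 people, and the only clash is 1 with 11. Both are filmed with probability *k*(*k* − 1)/(20 × 19):

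- *k* = 5: 20/380 = 0.053
- *k* = 10: 90/380 = 0.237
- *k* = 20: 380/380 = 1

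Mixed lengths need not clash. Codes 2 to 21 give 20 distinct names, because 11 is present but 1 is not, and 2 is present but 22 is not.

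**Step 3: three or four digits, issued at random without repeats.** With *n* possible names and *m* codes per name, P(at least one shared name) = 1 − C(*n*,*k*)·*m*^*k* / C(*nm*,*k*). For codes 000-999, *n* = 100 and *m* = 10. With *k* = 5 this is 1 − (1000/1000)(990/999)(980/998)(970/997)(960/996) = 0.087. Over the formats 000-999, 100-999, 0000-9999 and 1000-9999:

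| Filmed | P(at least one shared name) |
|---|---|
| 5 | 0.087 to 0.106 |
| 10 | 0.343 to 0.402 |
| 20 | 0.842 to 0.896 |

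Sequential codes such as 101 to 120 would give only 10 names for 20 people.

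**Step 4: which format does the text point to?** Three features stand together: 20 participants, an app that demands two name fields, and one digit placed in each field. Two digits suffice for 20 people, one digit does not, and nothing in the Protocol mentions three or more. The wording is how one would describe entering a two-digit code in a two-field form, which puts the text in Step 1.

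**Step 5: what would a shared name do?** It would not by itself cause an error. The paper forms and the spreadsheet hold app findings next to the other coded results, and recordings from different weekly sessions differ by date. If two participants' videos were nevertheless swapped within the same condition, the set of values in that condition would be unchanged. Its mean and spread would stay the same, and so would the difference between the two condition means. Only the spread of within-person changes, and any analysis joining video to other measures, would be altered.

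**The case for a change.** The strongest contrary case is that Sections 3.7 and 7.1 fix an explicit operating rule rather than leaving a detail to be settled later. Section 7.1 is meant to let another investigator repeat the study. A team that used three-digit codes would follow the text to the letter and could lose uniqueness, in a study that has deliberately removed faces, visible features and the link from person to code. Session dates do not fully rescue it: with three- or four-digit codes and all 20 participants filmed on days of 8, 8 and 4, the simulated chance of at least one same-day clash is 0.44 to 0.50. Stating the format would cost a few words.

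The logic stands, and the figures are right under their assumptions. What does not stand is the step from possible to likely. The large probabilities need two things that the Protocol does not support: codes longer than 20 people require, and high or full uptake of an optional procedure. They also measure shared names rather than mispairings; no probability of mispairing can be derived from the Protocol. Truncating a longer code could even serve privacy by making app videos harder to link to the study dataset, although the Protocol does not claim this. What is left is a code format that was not written down.

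**Conclusion.** No change to the plan follows. On the natural reading, a two-digit code split across the app's two name fields, every video carries its full code and the chance of a shared name is 0. The problem arises only with longer codes or some unpadded ones, and no section suggests that either is used. Even then the effect would be confined to the optional videos, might be resolved from forms, spreadsheet and session dates, and would leave the group summaries in each condition intact if videos were swapped within a condition.

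This rests on an inference about code length that the Protocol does not confirm. If staff did issue three-digit codes, the concern would become real for within-person and cross-measure analyses of the videos. Whoever draws up the code list for 20 people would be expected to settle the format sensibly, so this is missing detail rather than a fault in the design or analysis.
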